7. STUDY EVALUATIONS

A detailed scheduled examination components are shown by visit in Table 6.1.

7.1. Informed Consent

Consent to participate in a research study includes the elements listed below. The consent process will include all elements.

- Participants must be advised that the study involves research. Staff must explain the purposes of the research, the expected duration of participation, and a description of the procedures to be followed, including identification of experimental procedures.
- Anticipated benefits of the trial must be explained to the participant.
- Attendant discomforts and risks “reasonably to be expected” must be described.
- Appropriate alternative procedures that might be advantageous for the participant must be disclosed.
- The extent, if any, to which confidentiality of records identifying the participant will be maintained must be described.
- Prospective participants must be advised of the availability or non-availability of medical treatment or compensation for physical injuries incurred as a result of participation in the study, and if available, what they consist of, or where further information can be obtained.
- Persons responsible for the study must explain whom a participant can contact for answers to pertinent questions about the research and his or her rights, and whom to contact in the event of a research-related injury.
- Participants must be told that participation is voluntary, refusal to participate will involve no penalty or loss of benefits to which the participant is otherwise entitled, and the participant may discontinue participation at any time without penalty or loss of benefits to which he or she is otherwise entitled.

7.2. Eligibility Assessments

The objective of setting inclusion/exclusion criteria is to identify a trial population that will ensure adequate event rates for statistical power, provide maximum generalizability, and maximize safety. Inclusion criteria is defined in section 4.2, and exclusion criteria selected to enhance safety and adherence are defined in section 4.3. The following assessments are performed at screening visit to determine eligibility:

(1) Check Patients' Medical History: Eligible patients must have confirmed diagnoses of

hyperlipidemia according to European guidelines on cardiovascular disease prevention in clinical practice.

- (2) **Vital Signs:** Examination items include pulse rate, body temperature, respiratory rate, and blood pressure (including systolic blood pressure (SBP) and diastolic blood pressure (DBP)).
- (3) **Physical Examinations:** A physical examination will be completed and recorded in the source documents at Visit 1 prior to any study-related procedures. This evaluation will include an examination of general appearance, HEENT (head, eyes, ears, nose, and throat), mouth, skin, neck (including thyroid), lymph nodes, spine, cardiovascular system, respiratory system, gastro-intestinal system, nervous system, musculoskeletal system, blood and blood forming organs, mental status, and other body systems if applicable for describing the status of subject's health. Anthropometric measures gathered include standing height, weight, BMI, and waist circumference. Height is measured for the subject not wearing shoes at Visit 1. The measurement of height will be rounded to the nearest tenth of a centimeter. Body weight is measured for the subject not wearing shoes but wearing light clothing at Visit 1. The measurement of weight will also be rounded to the nearest tenth of a kilogram (if this procedure, measuring the height and weight, cannot be performed, obtaining this information from patients' medical chart (within 1 month) is acceptable). Other anthropometric measures include waist circumference and body mass index (BMI, calculated as kg/m^2) has been shown to be predictive of cardiovascular disease.
- (4) **Check Patients' Drug Records:** Check record of use of lipid-lowering drugs within 2 months. Patients taking lipid-lowering drugs shall have a 14-day wash-out period. In addition, patients shall not take any prohibited drugs mentioned in section 5.6.1 during the study period. If a subject is currently taking lipid-lowering drugs, the investigators shall determine whether discontinuation of these drugs will have impacts on his/her health status. If so, he/she is not recommended to enroll in the study.

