6.2.2. Enrollment/Randomization (Day 1)

Randomization Assessments at Visit 2

Once a patient has fulfilled the entry criteria, he/she will be randomized into either Antroquinonol 150 mg, Antroquinonol 100 mg, Antroquinonol 50 mg or placebo treatment group using a permuted block randomization method with 1: 1: 1: 1 ratio. The subject will be registered with a randomization number, and the study drug will be administered. The importance of compliance with study drug should be emphasized.

The assessments listed below will be performed. If the eligibility is confirmed and a wash-out period is not needed for the subject, based on investigator's judgements, the blood test, CT Scan, and Doppler color flow mapping required at visit 2 can be replaced by data obtained 14 days before V2.

- Physical examination
- Anthropometric measures (Height, weight, waist circumference, BMI)
- Vital signs (pulse rate, body temperature, respiratory rate, and blood pressure)

- Blood samples for
 - lipid profile (total cholesterol, TG, HDL-C, LDL-C and HDL-C /LDL-C ratio)
 - hematology (WBC, RBC, Hb, Hct, RDW, platelet, MCV, MCH, MCHC, neutrophil-band and segment, lymphocyte, monocyte, eosinophil, basophil)
 - serum chemistry (AST, ALT, CPK, BUN, serum creatinine, albumin, total bilirubin, direct bilirubin, ALP, total protein)
 - biomarkers (hsCRP, IL-1, IL-6, and TNF-alpha)
- 12-lead electrocardiogram
- Brachial-ankle pulse wave velocity (baPWV) and ankle-brachial index (ABI)
- Doppler color flow mapping, and CT scan of the liver
- Urinalysis
 - routine urine test (pH, protein, glucose, ketone, blood, urobilinogen, bilirubin, nitrite, leukocyte)
 - clinical microscopy

In addition, information on adverse events during the wash-out period and new concomitant medications will be collected.

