7.3. Demography Data and Medical History

- (1) **Date of Birth**
- (2) **Gender:** Male or Female
- (3) **Race**
- (4) **Medical History:** Review any diagnosis of liver or renal impairment, skin disorders or other severe diseases. Medical history data are collected at baseline in the form of a detailed initial medical history and collected at specified follow-up visits in the form of an abbreviated interval history. The medical history shall be reviewed thoroughly to ensure

that eligible patients don't have any symptoms/diseases specified in exclusion criteria (Section 4.3). Important aspects of the medical history include eligibility criteria, allergies, cardiovascular disease, smoking status, and diabetes. Any disease occurred within one year before visit 1 shall be recorded in CRF.

(5) Drug Records: Review and record drug medication within 2 months before patient enrollment till the end of the study. Information regarding the participants' concomitant medication therapy is collected and documented at baseline and then reviewed and revised at follow-up visits. Appropriate sources for obtaining this information include participant (significant other) report, current pharmacy action profiles, and verification of medications documented in the medical record. Although data are collected on all standing therapies, emphasis is placed on concurrent antihypertensive, glycemic and lipid-lowering therapy as well as background risk reduction (e.g., aspirin) therapy.

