9.2. Sample Size Considerations

The primary efficacy endpoint in this trial is “to compare the percentage change of triglyceride (TG) from baseline following a 12-week regimen of Antroquinonol versus placebo.” The objective of this trial is to assess the efficacy of the study treatment compared with control treatment. According to the literature review (FDA statistical reviews of Fibrate), the TG reduction percentage change of Fibrate from baseline to last visit was 36.6% for subjects who were treated with the study treatment, and 0.7% increased for the control treatment. According to prior published clinical reference, it is assumed that the mean TG percentage reduction is 27.5% and standard deviation is 40. The evaluable patient number should be at least 24 patients for each group under one-sided significance level 0.025 and power 90%. Considering a 20% drop-out rate, a sample size of 30 patients should be enrolled to each group, and a total of 120 patients will be recruited into this study. The sample size calculation was derived using PASS 2008.

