## 9.3 Primary Endpoint Analysis

The primary efficacy endpoint (percentage change of TG) for assessing the superiority of Antroquinonol (50mg, 100mg, 150mg) to placebo is the percentage change in patients with hyperlipidemia by using analysis of covariance (ANCOVA) model using baseline measurement as covariates (model 1). If the differences in baseline characteristics, such as gender, age, weight etc., are observed, for comparing the effectiveness between the treatment groups and placebo, the model will be performed by multiple linear model (model 2) to adjust characteristics.

Model 1:  $Y_{\text{percentage change of TG} (\%)} = \beta_1 + \beta_2 X_{\text{treatment}} + \beta_3 X_{\text{baseline of TG}}$

Model 2:  $Y_{\text{percentage change of TG} (\%)} = \beta_1 + \beta_2 X_{\text{treatment}} + \beta_3 X_{\text{baseline of TG}} + \beta_4 X_{\text{significant characteristic in baseline}}$

If statistical significance of ANCOVA treatment effect is reached ( $p\text{-value} < 0.05$ ), Bonferroni's method, and two independent t-test (section 7.7) will be performed post hoc analysis for pairwise comparison of percentage change in TG (Antroquinonol 50 mg vs. Placebo, Antroquinonol 100 mg vs. Placebo, Antroquinonol 150 mg vs. Placebo, Antroquinonol 100 mg vs. Antroquinonol 50 mg and Antroquinonol 150 mg vs. Antroquinonol 100 mg).

If the normal assumption is violated for percentage change of TG in any treatments, Kruskal-Wallis test will replace ANCOVA. If statistical significance of Kruskal-Wallis test treatment effect is reached ( $p\text{-value} < 0.05$ ), two independent t-test or Wilcoxon rank-sum test will be performed post hoc analysis for pairwise comparison of percentage change in TG (Antroquinonol 50 mg vs. Placebo, Antroquinonol 100 mg vs. Placebo, Antroquinonol 150 mg vs. Placebo, Antroquinonol 100 mg vs. Antroquinonol 50 mg and Antroquinonol 150 mg vs. Antroquinonol 100 mg).

Protocol: GHLIP-2-001

Study Sponsor: Golden Biotechnology Corporation

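### Wash-out status is known before randomisation and may predict TG change, but the primary model would include it only if an imbalance happened to be observed; it should be a prespecified covariate

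*Protocol*

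**What the plan says.** **Wash-out.** Protocol 7.2 (4) checks lipid-lowering drug use at screening: "Patients taking lipid-lowering drugs shall have a 14-day wash-out period". Protocol 7.3 (5) adds: "Review and record drug medication within 2 months before patient enrollment till the end of the study". The status is therefore on file before allocation.

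**Baseline sample.** Protocol 6.2.2 and note 3 to the flow chart in 6.1 let an earlier blood result stand in for the Visit 2 sample, but only where eligibility is confirmed and "a wash-out period is not needed for the subject". SAP 7.6 computes percentage change in TG from the Day 1 value.

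**Model.** SAP 9.3 specifies an "analysis of covariance (ANCOVA) model using baseline measurement as covariates (model 1"), with treatment and baseline TG as its only terms. Model 2 adds baseline characteristics if differences between arms are observed. Its examples are gender, age and weight, in an open-ended list. SAP 8.3 names concomitant medications among the baseline characteristics but not wash-out status, and SAP 8.5 sends prior-medication data to a listing.

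**Randomisation.** Protocol 4.5.1 and SAP 4.3 describe central permuted-block allocation, 1:1:1:1, with no stratification factor stated. SAP 4.3 describes the sequence as already generated.

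**Size.** Protocol 9.2: "The evaluable patient number should be at least 24 patients for each group under one-sided significance level 0.025 and power 90"%.

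**The concern.** The trial mixes patients who stopped a lipid-lowering drug shortly before Day 1 with patients who were not taking one. Their expected TG change without study drug need not be equal, for two reasons.

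- **Drug withdrawal.** TG may still be moving when the wash-out ends, and any remaining movement would be counted as on-study change.
- **Baseline source.** A patient without wash-out may have a baseline taken as early as screening (Day -14). That can be the same value that qualified the patient, so it is open to regression to the mean. It also precedes any effect of the diet and lifestyle counselling given at Visit 1 (Protocol 6.2.1). A wash-out patient has a separate Visit 2 sample.

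The same baseline TG may thus mean different things in the two groups, and one common baseline slope need not absorb the difference. If so, a pre-randomisation predictor is left in the error term, and a chance imbalance in it between small arms goes uncorrected.

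**Working it through.** **1. The plan's own figures.** Protocol 9.2 says "it is assumed that the mean TG percentage reduction is 27.5% and standard deviation is 40". For two means at one-sided 0.025 and 90% power:

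n per arm = 2(1.960 + 1.282)² × 40² / 27.5² = 44.5, so 45 (46 with the t distribution).

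The stated 24 is not reproduced. The cited literature difference ("36.6% for subjects who were treated with the study treatment, and 0.7% increased for the control treatment", that is 36.6 + 0.7 = 37.3) with SD 40 gives 25. The drop-out step does reproduce: 24 / 0.8 = 30 per arm, 120 in total. The shortfall against 45 is a separate matter. It is relevant here only because precision is scarce: with 24 per arm the standard error (SE) of a dose-placebo contrast is 40 × √(2/24) = 11.55 points, and power for 27.5 is Φ(27.5/11.55 − 1.96) = 66.3%.

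**2. Assumed inputs.** The documents give neither the wash-out share p nor the difference d in mean percentage change between wash-out and other patients. I take p = 20-50% and d = 10-30 points. For scale only, complete reversal of the 36.6% reduction quoted for a fibrate would be a rise of 1/0.634 − 1 = 58%. The drug mix and the movement left after Day 1 are unknown.

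**3. Gain from adjustment.** Formulas:
- variance explained R² = p(1−p)d²/40²
- adjusted SE = 11.55 × √(1−R²)
- SD of the chance shift in one contrast = d × √(2p(1−p)/24)

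| p, d | R² | SE reduction | Power at 27.5 | SD of chance shift |
|---|---|---|---|---|
| 20%, 10 | 1.0% | 0.5% | 66.8% | 1.15 points |
| 30%, 20 | 5.3% | 2.7% | 68.7% | 2.65 points |
| 50%, 20 | 6.3% | 3.2% | 69.1% | 2.89 points |
| 50%, 30 | 14.1% | 7.3% | 72.9% | 4.33 points |

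These figures give no credit to baseline TG and ignore the cost of the extra term. With 96 evaluable patients Model 1 has 96 − 4 − 1 = 91 error df. One more term costs roughly 1/91 = 1.1% in variance, which cancels the gain in the first row.

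**4. The last column is not an extra error.** (1.15/11.55)² = 0.010 and (4.33/11.55)² = 0.141, which are the R² values again. The chance shift is already contained in the SD of 40.

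**5. Would Model 2 catch it?** By simulation with 24 per arm, a gap of at least 20 percentage points in wash-out share between placebo and at least one dose arm occurs in about 30% (p = 25%) to 42% (p = 50%) of trials. A four-arm chi-square test at 0.05 flags an imbalance in only about 5%.

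**The case against.** **No stated effect.** A reader might infer that wash-out status is a known predictor, or that the design builds in a TG drift. The documents support neither: no section says that TG is still moving after the wash-out or sizes any movement. If TG has settled by Day 1, the drug-withdrawal part is zero. What the design does build in is the wash-out itself and the different rule for the baseline sample. This objection stands, and it is why the point is worded as a possibility.

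**Not absent from every model.** Model 2's open list could admit wash-out status. That is correct, but the rule depends on an observed difference, does not name the factor and would seldom trigger.

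**Small gain.** For differences up to 20 points the power gain is under 3 percentage points, and baseline TG may absorb part of it. This stands.

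**Limited reach.** A term in Model 1 does not affect the separate pairwise t-tests of SAP 7.7 and 9.3 or the Kruskal-Wallis fallback. The t-tests can be dealt with by taking contrasts from the model; the fallback cannot.

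**Loose definition.** Protocol 4.2 (3) speaks of patients previously treated and 7.2 (4) of patients taking such drugs. A yes/no term also pools drug classes, and it marks baseline timing only partly, because using the earlier sample is optional. A definition has to be written.

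**Conclusion.** The point holds as a low-cost improvement in precision. Wash-out status is collected before randomisation, may predict the outcome, is not in Model 1, and would reach Model 2 only on an observed imbalance. Under the assumed share of 20-50% and difference of 10-30 points with SD 40, adjustment removes 1% to 14% of outcome variance and narrows the SE by about 0.5% to 7%. Both inputs are assumptions, and the lower end is worth nothing after the cost of the term.

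Two stronger readings are not supported. One is that the dose-placebo comparison is biased: randomisation keeps it unbiased on average. The other is that chance imbalance adds up to 8.7 points (2 × 4.33, the extreme corner) on top of the reported uncertainty: that shift is already within the SE of 11.55. Nor does adjustment repair the sample size: at p = 50% and d = 30, 39 per arm would still be needed for 90% power. The lipid secondary endpoints follow the same reasoning, but I have made no calculation for them.

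**What to change.** Before unblinding:

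1. Define wash-out status (lipid-lowering drug stopped for the 14-day wash-out, yes/no) from the recorded prior-medication data. State how patients who stopped within the two recorded months but before screening are classified.
2. Enter it as a fixed, prespecified covariate in SAP 9.3 Model 1 and in the TC, HDL-C, LDL-C and LDL/HDL ANCOVAs of SAP 9.4, whatever the baseline comparison shows.
3. Take the dose-placebo contrasts from that adjusted model, with the Bonferroni rule of SAP 9.7 unchanged for TG, rather than from separate t-tests.

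The cost is about 1 of 91 error df and no new data. The gain is near zero if few patients need wash-out, and nil if the Kruskal-Wallis fallback is used. Added after unblinding, the term would be a post-hoc choice. No change to randomisation is proposed, since the sequence is already generated.

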7.3. Demography Data and Medical History

- (1) **Date of Birth**
- (2) **Gender:** Male or Female
- (3) **Race**
- (4) **Medical History:** Review any diagnosis of liver or renal impairment, skin disorders or other severe diseases. Medical history data are collected at baseline in the form of a detailed initial medical history and collected at specified follow-up visits in the form of an abbreviated interval history. The medical history shall be reviewed thoroughly to ensure

that eligible patients don't have any symptoms/diseases specified in exclusion criteria (Section 4.3). Important aspects of the medical history include eligibility criteria, allergies, cardiovascular disease, smoking status, and diabetes. Any disease occurred within one year before visit 1 shall be recorded in CRF.

(5) Drug Records: Review and record drug medication within 2 months before patient enrollment till the end of the study. Information regarding the participants' concomitant medication therapy is collected and documented at baseline and then reviewed and revised at follow-up visits. Appropriate sources for obtaining this information include participant (significant other) report, current pharmacy action profiles, and verification of medications documented in the medical record. Although data are collected on all standing therapies, emphasis is placed on concurrent antihypertensive, glycemic and lipid-lowering therapy as well as background risk reduction (e.g., aspirin) therapy.

7.4. Urine Pregnancy Test/Contraception Methods

7.4.1. Urine pregnancy test

All the female subjects with childbearing potential must perform urine pregnancy test (or serum pregnancy test if urine is not available) at the screening visit, and they should avoid pregnancy during this trial. Subjects must be permanently discontinued if pregnancy is confirmed by a positive urine (or serum) pregnancy test. Notably, subject shall avoid pregnancy using an efficient contraception method (recommendation listed in **Section 7.4.2**, including but not limited to) during the entire 16 weeks of the study. Once any pregnancy event is known during the study, this pregnant subject must be withdrawn from the study immediately, and will be followed up. Pregnancies and pregnancy follow-up should be reported on the Adverse Event Form. Pregnancy follow-up should describe the outcome of the pregnancy, including any voluntary or spontaneous termination, details of the birth, the presence or absence of any congenital abnormalities, birth defect, maternal or newborn complications. Monitoring of the patient should continue until conclusion of the pregnancy.

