6.2. Study Procedures

6.2.1. Screening (Day -14)

All patients must provide written informed consent before any study specific assessments or procedures are performed. A subject enrollment form documenting the investigator's assessment of each screened subject with regard to the protocol's inclusion and exclusion criteria has to be completed by the investigator.

Based on the results of Visit 1 assessments (see below 'Screening Assessments at Visit 1'), potentially eligible patients will enter a wash-out period as necessary. Blood test data generated by the study site or central laboratory 3 days prior to Visit 1 can be accepted.

Screening Assessments at Visit 1

- Demographics, medical history, including previous and concomitant diseases and treatments
- Physical examination
- Anthropometric measures (Height, Weight, Waist circumference, BMI)
- Vital signs (pulse rate, body temperature, respiratory rate, and blood pressure)
- Urine Pregnancy Test
- Blood samples for
 - lipid profile (total cholesterol, TG, HDL-C, LDL-C and LDL/HDL ratio)
 - biochemistry (serum creatinine for estimating GFR)

Patients will be instructed to come in fasted state for all subsequent study visits. Patients should receive information on a heart healthy diet and counseling on lifestyle changes as appropriate.

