6.2.3. On treatment visits (Day 29±3, Day 57±3, Day 85±3)

During the treatment period, subjects will visit the clinic every 4 weeks. Subjects have to come in fasted state for all visits. Therefore, subjects will be instructed not to take study drug in the morning of study visits but to wait until all study assessments have been completed. Subjects will receive new drug supply at each visit and will be required to bring in all unused study drugs for assessment of compliance.

Treatment Period Assessments at Visit 3 and 4 (± 3 days)

The following evaluations will be performed at each visit throughout treatment:

- Physical examination
- Anthropometric measures (Height, weight, waist circumference, BMI)
- Vital signs (pulse rate, body temperature, respiratory rate, and blood pressure)
- Blood samples for
 - lipid profile (total cholesterol, TG, HDL-C, LDL-C and LDL/HDL ratio)
 - serum chemistry (AST, ALT, CPK, BUN, serum creatinine)
- Information on adverse events
- Information on new concomitant medications
- Record of drug dispense and drug return

End of Treatment Assessments at Visit 5 (± 3 days)

The following evaluations will be performed:

- Physical examination
- Anthropometric measures (Height, weight, waist circumference, BMI)
- Vital signs (pulse rate, body temperature, respiratory rate, and blood pressure)
- Blood samples for
 - lipid profile (total cholesterol, TG, HDL-C, LDL-C and LDL/HDL ratio)
 - hematology (WBC, RBC, Hb, Hct, RDW, platelet, MCV, MCH, MCHC, neutrophil-band and segment, lymphocyte, monocyte, eosinophil, basophil)
 - serum chemistry (AST, ALT, CPK, BUN, serum creatinine, albumin, total bilirubin, direct bilirubin, ALP, total protein)
 - biomarkers (hsCRP, IL-1, IL-6, and TNF-alpha)
- 12-lead electrocardiogram
- Brachial-ankle pulse wave velocity (baPWV) and ankle-brachial index (ABI)
- Doppler color flow mapping, and CT scan of the liver for patients with confirmed fatty liver at Visit 2
- Urinalysis
 - routine urine test (pH, protein, glucose, ketone, blood, urobilinogen, bilirubin, nitrite, leukocyte)
 - clinical microscopy
- Information on adverse events
- Information on new concomitant medications
- Record of drug return

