6.2.5. Early termination visit /Withdrawal visit

For subjects who prematurely withdraw from treatment, the same procedures as the one at the end of the treatment will be applied. An end of treatment visit should be scheduled as soon as possible and the assessments listed below should be performed. Subjects will be required to bring in all study drugs for assessment of compliance. If the decision of discontinuation is being taken while the subject is in the clinic for a visit, the end of treatment assessments may be performed on that day.

- Physical examination
- Anthropometric measures (Height, weight, waist circumference, BMI)
- Vital signs (pulse rate, body temperature, respiratory rate, and blood pressure)
- Blood samples for
 - lipid profile (total cholesterol, TG, HDL-C, LDL-C and LDL/HDL ratio)
 - hematology (WBC, RBC, Hb, Hct, RDW, platelet, MCV, MCH, MCHC, neutrophil-band and segment, lymphocyte, monocyte, eosinophil, basophil)
 - serum chemistry (AST, ALT, CPK, BUN, serum creatinine, albumin, total bilirubin, direct bilirubin, ALP, total protein)
 - biomarkers (hsCRP, IL-1, IL-6, and TNF-alpha)
- 12-lead electrocardiogram
- Brachial-ankle pulse wave velocity (baPWV) and ankle-brachial index (ABI)
- CT scan of the liver for patients with confirmed fatty liver at Visit 2
- Urinalysis
 - routine urine test (pH, protein, glucose, ketone, blood, urobilinogen, bilirubin, nitrite, leukocyte)
 - clinical microscopy
- Information on adverse events
- Information on new concomitant medications

A safety follow-up should be conducted for subjects who prematurely withdraw from treatment

2 weeks after the end of treatment visit. A clinic visit is recommended unless the subject refused to return. If so, the safety follow-up may be conducted via telephone.

Subjects willing to provide information should be followed for assessments of adverse events until the end of the trial. At a minimum, the investigator should make every effort to obtain information on whether or not the subject is alive or dead at the end of the study.

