7.5. Laboratory Evaluations

7.5.1 Clinical laboratory evaluations

Laboratory tests (including hematology, biochemistry, and urinalysis) will be scheduled as below. The examination items are included in **Table 7- 1**.

Lipid Profile: Blood samples to assess total cholesterol, triglycerides, HDL-C, LDL-C, LDL/HDL ratio will be obtained from visit 1 to visit 5.

Hematology: Blood samples to assess WBC, RBC, Hb, Hct, RDW, platelet, MCV, MCH, MCHC, neutrophil-band and segment, lymphocyte, monocyte, eosinophil, basophil will be obtained at visit 2 and visit 5.

Serum Biochemistry: Blood samples to assess AST, ALT, CPK, BUN and serum creatinine will be obtained from visit 2 to visit 5, albumin, total bilirubin, direct bilirubin, ALP, total protein will be obtained at visit 2 and visit 5. At screening visit, serum creatinine shall be run for estimating glomerular filtration rate (GFR).

Urinalysis: Assessments of urine pH, protein, glucose, ketone, blood, urobilinogen, bilirubin, nitrite, leukocyte and clinical microscopy will be tested at visit 2 and visit 5.

Pregnancy Test: Urine HCG test will be performed at visit 1.

12-lead ECG: ECG will be performed in accordance with the standard procedures at the site at visit 2 and visit 5.

baPWV and ABI measurement: baPWV is used to assess arterial stiffness and will be

obtained using VP 1000 or VP 1000 plus (Omron) at visit 2 and visit 5/early termination visit. ABI is a surrogate marker of atherosclerosis and will be obtained using the same device at visit 2 and visit 5/early termination visit.

Echocardiography: Values for S', E', and A' will be measured and averaged over three consecutive cardiac cycles. A composite mean for each of these parameters is then formed by taking the average of the values from the septal, lateral, and inferior wall. The ratio of the transmitral Doppler E wave velocity and the composite mean of E' will then be used to calculate the E/E' ratio. E/E' ratio will be obtained at visit 2 and visit 5.

CT scan of the liver: Each participant will undergo non-enhanced liver computed tomography (CT) scans at visit 2. The Hounsfield Unit (HU) attenuation of liver on CT scans will be utilized for determination of fatty liver (L/S ratio <1.0 and liver attenuation <40HU). Subjects who are confirmed with fatty liver will undergo liver CT scans again at visit 5.

Table 7- 1 Laboratory tests planned to be performed

Hematology	Biochemistry	Urinalysis	Others

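### The mandatory pregnancy withdrawal and the withdrawal-visit procedures together order a liver CT for a subject known to be pregnant who had fatty liver at Visit 2, because no exception is stated

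*Protocol*

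**What the plan says.** **Withdrawal on pregnancy.** Protocol section 7.4.1 provides that once a pregnancy becomes known, "this pregnant subject must be withdrawn from the study immediately, and will be followed up". Section 8.4.2 states the same duty, to be carried out promptly.

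**What happens at withdrawal.** Section 6.2.5 states: "For subjects who prematurely withdraw from treatment, the same procedures as the one at the end of the treatment will be applied". The visit is to take place as soon as possible, and its list includes "CT scan of the liver for patients with confirmed fatty liver at Visit 2". Section 4.5.5 also asks for a complete final evaluation when a subject withdraws.

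**Scheduled CTs.** Section 7.5.1 gives every participant a non-enhanced liver CT at Visit 2. It adds: "Subjects who are confirmed with fatty liver will undergo liver CT scans again at visit 5". The flow chart in section 6.1 carries the same fatty-liver condition for Visit 5 and accepts a baseline CT taken between Visits 1 and 2.

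**Pregnancy testing.** Section 7.4.1 requires that "All the female subjects with childbearing potential must perform urine pregnancy test" at screening, and section 7.5.1 states "Urine HCG test will be performed at visit 1". The flow charts in the protocol and the SAP mark the test at Visit 1 only. No test is listed for Visits 2 to 6, the withdrawal visit or unscheduled visits.

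**The concern.** Each rule is reasonable alone. The difficulty comes from applying both to the same person. Pregnancy triggers withdrawal, withdrawal triggers the end-of-treatment list, and that list contains a CT. The CT line is already restricted by fatty-liver status, so its scope was considered, but pregnancy is not mentioned.

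At stake is an avoidable radiation exposure in a known pregnancy, for an imaging endpoint that serves the trial and not the subject's care. This does not fit the protocol's own caution elsewhere: pregnant women are excluded at entry (section 4.3), and section 7.4.2 warns participants of unknown fetal risk from the study medication. The scan also has little analytic return. Section 9.5 of the protocol censors values measured after study drug is stopped and imputes nothing for secondary endpoints.

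**Working it through.** **1. The rules side by side**

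| Step | Rule | Source (protocol) | Pregnancy exception? |
|---|---|---|---|
| Pregnancy becomes known | Withdraw at once | 7.4.1, 8.4.2 | Not applicable |
| Subject leaves treatment early | End-of-treatment procedures, as soon as possible | 6.2.5 | None |
| Fatty liver confirmed at Visit 2 | Liver CT at that visit | 6.2.5 | None |

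The CT is ordered only when all of these hold: the pregnancy becomes known before treatment is complete, so that the withdrawal is premature; and fatty liver was confirmed at Visit 2. A pregnant subject without fatty liver is not sent to CT by this route.

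**2. Timing of the single test**

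Inputs: Visit 1 at Day -14, Visit 2 at Day 1, Visit 5 at Day 85 ± 3, Visit 6 at Day 99 (sections 6.1 and 6.2). The lower figure in each pair assumes that there is no Day 0.

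- Check against the plan's own figure: Visit 1 to Visit 6 is 99 + 14 = 113 days, or 112 without a Day 0. Dividing by 7 gives 16.1 or 16.0 weeks, which agrees with the stated 16 weeks of participation.
- Test to Visit 2 CT: 1 + 14 = 15 days, or 14; that is 2.1 or 2.0 weeks. This is the scheduled interval, and it is shorter if the CT is taken between Visits 1 and 2, as the flow chart allows.
- Test to Visit 5 CT: 85 + 14 = 99 days, or 98; that is 14.1 or 14.0 weeks. With the visit window, 98 - 3 = 95 to 99 + 3 = 102 days, or 13.6 to 14.6 weeks.

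**3. How many subjects?**

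The number of CTs ordered in this way would be

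(women of child-bearing potential) × (chance of a pregnancy becoming known before the end of treatment) × (share with fatty liver at Visit 2).

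The documents give neither the first term nor the third. For the first two terms only, assume 12 to 30 such women among 120 and take 16/52 = 0.31 year:

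- At 1% failure per year (the benchmark in section 7.4.2): 12 × 0.01 × 0.31 = 0.04 to 30 × 0.01 × 0.31 = 0.09 pregnancies.
- At an assumed 15% per year with 30 women: 30 × 0.15 × 0.31 = 1.4 pregnancies.

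These are pregnancies under assumed inputs, not CT exposures. Exposures would be fewer, because the fatty-liver share has not been applied and the 16 weeks include follow-up after treatment.

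**4. What the withdrawal CT adds to the analysis**

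For efficacy it adds little, given the censoring rule in section 9.5. It is not certain to add nothing. Section 6.2.5 lets the assessments be done on the day of the decision, so whether the scan counts as after termination can be argued. SAP section 7.3 does not repeat the censoring rule, and SAP Tables 14.4.3.1 to 14.4.3.3 list HU in the Safety Population.

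**The case against.** **An investigator would simply omit the scan.** That is likely, but the text does not provide for it. Section 10.7 treats any noncompliance with the protocol as a deviation to be recorded and sent to the ethics committee, so omitting the scan would count as one. The documents describe no imaging safeguard that would settle the matter.

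**Withdrawal from the study could mean that no further procedures apply, since section 6.2.5 speaks of leaving treatment.** The wording differs, but a subject withdrawn from the study also stops treatment. Section 4.5.5 asks for a full evaluation at withdrawal, and section 6.2.5 is itself titled as the withdrawal visit. The reading is possible but is nowhere stated.

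**Contraception is required and the event is rare.** This stands as a limit on size. It is not a check before CT, and sections 7.4.1 and 8.4.2 themselves plan for pregnancies.

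**The pregnancy rule does not need a repeat test.** This also stands. A reader might infer that withdrawal can follow only a positive test. Section 7.4.1 acts on any pregnancy that becomes known, and the interval history (section 7.3) and the adverse-event enquiry at each visit (section 7.6) are other routes to that knowledge.

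**The single test is consistent throughout.** Correct. The protocol and SAP agree on Visit 1, and no passage promises another test. A reader might take the test timing as a second contradiction, but the documents do not support that. It is an observation about what the pregnancy rule relies on.

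**Conclusion.** The conflict holds on the text. Sections 7.4.1 and 8.4.2, read with section 6.2.5, order a research CT for a subject known to be pregnant who had fatty liver confirmed at Visit 2 and whose treatment was not complete. Applying the stated rules gives the worse patient-safety result, so this is more than a missing detail.

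The size is probably very small and cannot be computed from the documents. The importance of the point rests on the exposure being avoidable, not on its frequency.

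Three stronger readings are tempting but unsupported:

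- A reader might infer that every pregnancy in the trial leads to CT. At withdrawal and at Visit 5 the scan is limited to subjects with confirmed fatty liver. Only the Visit 2 CT is unconditional.
- A reader might infer that section 7.5.1 also orders the withdrawal CT. Its CT paragraph names only Visits 2 and 5, whereas its paragraph on baPWV and ABI does name the early termination visit. The withdrawal CT rests on section 6.2.5.
- A reader might infer that dropping the scan would cost no data at all. For the reasons in step 4 of the working, a few HU values could still appear in safety tables.

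As a secondary observation, the pregnancy rule depends on pregnancy becoming known by routes other than scheduled testing for the 98 to 99 days between the Visit 1 test and the Visit 5 CT, and for up to about 2 weeks before the Visit 2 CT.

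**What to change.** Reconcile section 6.2.5 with sections 7.4.1 and 8.4.2 so that the protocol states whether the withdrawal-visit CT applies to a subject withdrawn for pregnancy. Separately, ask the sponsor's medical staff to review the timing of the pregnancy test against the CT dates in sections 6.1, 6.2.3 and 7.5.1 and to record the outcome. The clinical rule in both cases is for the sponsor and investigator to set; none is proposed here.

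The cost of the first change is about one sentence in section 6.2.5, with a cross-reference from sections 7.4.1 and 8.4.2, processed as an amendment under section 13.5. Whichever way the rule is set, the effect on the fatty-liver efficacy analysis should be slight under section 9.5. If the SAP is revised for any other reason, its missing-data section should say whether the section 9.5 censoring rule applies to HU, including in the safety tables.
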